6.9.1.1.2. Infusion-Related Reactions-Pembrolizumab

Table JVDF.5 presents pembrolizumab dose modification and supportive care guidelines for patients who experience an IRR associated with pembrolizumab. For Grade 3-4 IRRs, the patient is immediately and permanently discontinued from pembrolizumab.

6.9.1.2. Supportive Care for Ramucirumab

6.9.1.2.1. Supportive Care by Adverse Event of Special Interest

6.9.1.2.1.1. Hypertension

An increased incidence of severe hypertension (CTCAE Grade 3) has been reported in patients receiving ramucirumab compared with placebo. In most cases, hypertension was controlled using standard antihypertensive treatment. Preexisting hypertension should be controlled before starting ramucirumab treatment.

Monitoring of blood pressure is required during, and should occur prior to, ramucirumab therapy. Every attempt should be made to control blood pressure to systolic <140 mm Hg and diastolic <90 mm Hg prior to starting treatment with ramucirumab. Routine clinical and laboratory monitoring is required in patients who again develop hypertension or experience a deterioration in previous hypertension.

6.9.1.2.1.2. Proteinuria

Proteinuria is an adverse effect for all therapies targeting the VEGF/VEGF Receptor 2 pathway, including ramucirumab. In ramucirumab clinical trials, the majority of events were Grade 1 or 2. Monitoring for the development or worsening of proteinuria during ramucirumab therapy is required. Discontinue ramucirumab if the patient experiences proteinuria >3 g/24 hours or nephrotic syndrome.

6.9.1.2.1.3. Thromboembolic Events

6.9.1.2.1.3.1. Arterial Thromboembolic Events

Serious, sometimes fatal arterial thromboembolic events, including myocardial infarction, cardiac arrest, cerebrovascular accident, and cerebral ischemia, have been reported in clinical trials.

6.9.1.2.1.3.2. Venous Thromboembolic Events

Venous thromboembolic events are associated with cancer; however, the incidence of VTEs likely varies depending on the type of cancer, stage, and intensity of imaging. Additionally, VTEs have been associated with some antiangiogenic therapy, although the incidence varies depending on the type of therapy, use of concomitant chemotherapy agents, and specific disease state. VTEs have been reported from clinical studies investigating ramucirumab, particularly in the context of metastatic disease or in regions adjacent to implanted venous access devices.

6.9.1.2.1.4. Bleeding/Hemorrhage

Ramucirumab is an antiangiogenic therapy and has the potential to increase the risk of severe bleeding. Severe GI hemorrhages, including fatal events, have been reported in patients with gastric-GEJ cancer treated with ramucirumab in combination with paclitaxel.

Serious hemorrhagic AEs have been reported from clinical studies investigating ramucirumab. Hemorrhagic complications are associated with some malignancies (that is, variceal bleeding from portal hypertension in hepatocellular carcinoma, lower GI hemorrhage from bowel metastases in ovarian carcinoma), although the rate of these complications varies considerably. As detailed in the ramucirumab IB, the incidences of hemorrhagic events to date, significant background incidence of bleeding in some malignancies, and use of concomitant antiplatelet therapy in some of the reported cases preclude any definitive association between bleeding and ramucirumab, although ongoing surveillance and identification (and exclusion) of patients with high bleeding risk remain essential and are detailed in the inclusion/exclusion criteria.

6.9.1.2.1.5. Gastrointestinal Perforation

Patients with unresected (or recurrent) primary tumors or mesenteric or peritoneal disease who participate in this clinical study may be at increased risk for GI perforation due to the nature of the disease (metastatic gastric-GEJ cancer).

An infrequent incidence of GI perforations has been associated with some antiangiogenic therapeutic agents, most specifically in the context of colorectal cancer (treated with combination regimens, including anti-VEGF antibodies and cytotoxic chemotherapy) and in advanced ovarian cancer. These events may be associated with extensive abdominal/peritoneal disease burden. Gastrointestinal perforation has been reported from clinical studies investigating ramucirumab. The incidences of these events to date and presence of significant comorbidities and risk factors preclude any definitive association with ramucirumab, although ongoing surveillance remains essential. More information about GI perforation may be found in the IB.

6.9.1.2.1.6. Reversible Posterior Leukoencephalopathy Syndrome

Reversible posterior leukoencephalopathy syndrome (RPLS) is a clinical and radiologic syndrome typically consisting of reversible cortical neurological dysfunction and brain-imaging findings of subcortical edema involving the posterior circulation, particularly the occipital lobes (Hinchey et al. 1996). The symptoms of RPLS most often include generalized seizures, headache, delirium, and cortical blindness, although these may vary significantly and occasionally include focal neurological deficits (Hinchey et al. 1996; Garg 2001; Lee et al. 2008). MRI represents the most reliable method for diagnosis (Lee et al. 2008). Clinical symptoms and MRI abnormalities usually recover within days to weeks with proper management, although permanent neurologic dysfunction has been reported (Hinchey et al. 1996; Tajima et al. 1999; Garg 2001; Lee et al. 2008).

Across the clinical program to date, 2 cases of RPLS have been reported: One case occurred in each arm of the recently completed double-blind, randomized, placebo-controlled Phase 3 Study RAISE evaluating ramucirumab in combination with FOLFIRI versus FOLFIRI in combination with placebo for patients with metastatic colorectal cancer.

RPLS should be identified and treated promptly in order to minimize potential for permanent neurological damage. Treatment encompasses careful control of blood pressure, withdrawal of potentially causative medication, and administration of anticonvulsant agents to those experiencing seizures (Stott et al. 2005).

6.9.1.2.1.7. Congestive Heart Failure

An increased risk of congestive heart failure (CHF) has been associated with some antiangiogenic therapeutic agents, particularly in patients with metastatic breast cancer previously treated with anthracyclines. A small number of CHF events (including fatal) were also reported in patients who had received ramucirumab after prior treatment with anthracyclines in the Phase 2 and Phase 3 studies.

Patients with risk factors should be closely monitored for signs and symptoms of CHF.

Caution should be exercised when treating patients with clinically significant cardiovascular disease, such as preexisting coronary artery disease or CHF. Ramucirumab should be discontinued in the event of any Grade 3 or 4 events consistent with CHF.

6.9.1.2.1.8. Fistula Formation

Because fistula formation has been associated with antiangiogenic agents, patients may be at increased risk for the development of fistula when treated with ramucirumab. Some fistulas can be resolved with surgical procedures; however, fistulas can be fatal. The impact on the quality of life of having a fistula varies according to the location and extent of the fistula (Chen and Cleck 2009).

6.9.1.2.1.9. Surgery and Impaired Wound Healing

Because ramucirumab is an antiangiogenic therapy, it may have the potential to adversely affect wound healing. Ramucirumab did not impair wound healing in a study conducted in animals; however, the impact of ramucirumab on serious or nonhealing wounds has not been evaluated in humans.

6.9.1.2.1.10. Liver Failure and Other Significant Liver Injury

Liver failure or other significant liver injury events, such as hepatic encephalopathy, have been observed in patients receiving ramucirumab. Patients with 1) cirrhosis at a level of Child-Pugh Class B (or worse) or 2) cirrhosis (any degree) and a history of hepatic encephalopathy or clinically meaningful ascites resulting from cirrhosis should not be enrolled in clinical trials with ramucirumab. “Clinically meaningful ascites” is defined as ascites resulting from cirrhosis and requiring ongoing treatment with diuretics and/or paracentesis. See Site Guidance document for Hepatic Monitoring/Drug-Induced Liver Injury.

6.9.1.2.2. Supportive Care Agents for Ramucirumab- Guidelines

Supportive care measures may include but are not limited to antiemetic agents, opiate and nonopiate analgesic agents, appetite stimulants, and granulocyte and erythroid growth factors. Guidelines regarding the use of specific supportive care agents are presented below.

6.9.1.2.2.1. Antiemetic Agents

Although emesis is not an expected side effect of ramucirumab, the use of antiemetic agents is permitted at the discretion of the investigator. Acceptable antiemetic agents include 5-HT₃ receptor antagonists (for example, ondansetron), dopamine receptor antagonists (for example, metoclopramide), corticosteroids (for example, dexamethasone), and others.

6.9.1.2.2.2. Analgesic Agents

The use of analgesic agents is permitted at the discretion of the investigator. Opiate and nonopiate analgesic agents are permitted (including acetaminophen/paracetamol); however, use of NSAIDs and/or aspirin is restricted ([Attachment 7](#)).

6.9.1.2.2.3. Appetite Stimulants

The use of appetite stimulants is permitted at the discretion of the investigator. Examples include megestrol acetate, dronabinol, and others.

6.9.1.2.2.4. Granulocyte-Colony Stimulating Factors

The as-needed use of G-CSFs is permitted at the discretion of the investigator based on American Society of Clinical Oncology (ASCO) guidelines (Smith et al. 2006) ([Attachment 7](#)).

6.9.1.2.2.5. Erythroid Growth Factors

The as-needed use of erythroid-stimulating factors (for example, erythropoietin) is permitted at the discretion of the investigator based on ASCO guidelines (Rizzo et al. 2008) ([Attachment 7](#)).

6.9.1.2.2.6. Other Supportive Care Agents

The use of benzodiazepines, antidepressants, laxatives, and other agents that may be helpful in controlling disease-related symptoms are also permitted and encouraged, except as prohibited in [Attachment 7](#).

6.9.1.3. Supportive Care for Pembrolizumab

Supportive care guidelines for the management of specific AEs with potential immunologic etiology are outlined below. Where appropriate, these guidelines include the use of oral or intravenous treatment with corticosteroids as well as additional anti-inflammatory agents if symptoms do not improve with administration of corticosteroids. Several courses of steroid tapering may be necessary, as symptoms may worsen when the steroid dose is decreased. For each disorder, attempts should be made to rule out other causes such as metastatic disease or bacterial or viral infection, which might require additional supportive care. The treatment guidelines are intended to be applied when the investigator determines the events to be related to pembrolizumab.

If after the evaluation the event is determined not to be related, the investigator does not need to follow the treatment guidance as outlined below.

It may be necessary to perform conditional procedures such as bronchoscopy, endoscopy, or skin photography as part of evaluation of the event.

6.9.1.3.1. *Pneumonitis - Pembrolizumab*

Apply the following supportive care guidance for pneumonitis:

For Grade 2 events, treat with systemic corticosteroids (prednisone 1 to 2 mg/kg/day or equivalent). When symptoms improve to Grade 0-1, steroid taper should start and be continued over no less than 4 weeks.

For Grade 3-4 events, immediately treat with intravenous steroids (methylprednisolone 125 mg followed by high-dose oral steroids (prednisone 1 to 2 mg/kg/day or dexamethasone 4 mg every 4 hours). Administer additional anti-inflammatory measures, as needed.

Add prophylactic antibiotics for opportunistic infections, in the case of prolonged steroid administration.

6.9.1.3.2. *Diarrhea/Colitis - Pembrolizumab*

Patients should be monitored carefully for signs and symptoms of enterocolitis (such as diarrhea, abdominal pain, and blood or mucus in stool, with or without fever) and of bowel perforation (such as peritoneal signs and ileus).

- All patients who experience diarrhea/colitis should be advised to drink liberal quantities of clear fluids. If sufficient oral fluid intake is not feasible, fluid and electrolytes should be substituted via IV infusion. For Grade 2 or higher diarrhea, consider GI consultation and endoscopy to confirm or rule out colitis.
- For **Grade 2 diarrhea/colitis**, administer oral corticosteroids (prednisone 1 to 2 mg/kg/day or equivalent).
- For **Grade 3 or 4 diarrhea/colitis (or Grade 2 diarrhea)**, treat with intravenous steroids (methylprednisolone 125 mg) followed by high-dose oral steroids (prednisone 1 to 2 mg/kg/day or dexamethasone 4 mg every 4 hours).
- When symptoms improve to Grade 1 or less, steroid taper should be started and continued over no less than 4 weeks.

6.9.1.3.3. *Type 1 Diabetes Mellitus or Hyperglycemia - Pembrolizumab*

For Grade 3-4 hyperglycemia or new onset type 1 diabetes mellitus (T1DM), including diabetic ketoacidosis (DKA) or \geq Grade 3 hyperglycemia, if associated with ketosis (ketonuria) or metabolic acidosis (DKA), supportive care guidance is as follows:

- Insulin replacement therapy is recommended for T1DM and for Grade 3-4 hyperglycemia associated with metabolic acidosis or ketonuria.
- Evaluate patients with serum glucose and a metabolic panel, urine ketones, glycosylated hemoglobin, and C-peptide.

6.9.1.3.4. *Hypophysitis - Pembrolizumab*

Apply the following supportive care guidance for hypophysitis:

- For **Grade 2** events, treat with corticosteroids. When symptoms improve to Grade 1 or less, steroid taper should be started and continued over no less than 4 weeks. Replacement of appropriate hormones may be required as the steroid dose is tapered.

- For **Grade 3-4** events, treat with an initial dose of IV corticosteroids followed by oral corticosteroids. When symptoms improve to Grade 1 or less, steroid taper should be started and continued over no less than 4 weeks. Replacement of appropriate hormones may be required as the steroid dose is tapered.

6.9.1.3.5. *Hyperthyroidism or Hypothyroidism - Pembrolizumab*

Thyroid disorders can occur at any time during treatment. Monitor patients for changes in thyroid function (at the start of treatment, periodically during treatment, and as indicated based on clinical evaluation) and for clinical signs and symptoms of thyroid disorders. Apply the following supportive care guidance:

- **Grade 2** hyperthyroidism events and **Grade 2-4** hypothyroidism:
 - In hyperthyroidism, non-selective beta-blockers (for example, propranolol) are suggested as initial therapy.
 - In hypothyroidism, thyroid hormone replacement therapy, with levothyroxine or liothyroinine, is indicated per standard of care.
- **Grade 3-4** hyperthyroidism
 - Treat with an initial dose of IV corticosteroid followed by oral corticosteroids. When symptoms improve to Grade 1 or less, steroid taper should be started and continued over no less than 4 weeks. Replacement of appropriate hormones may be required as the steroid dose is tapered.

6.9.1.3.6. *Hepatic Events - Pembrolizumab*

See Site Guidance Document for Hepatic Monitoring/Drug-Induced Liver Injury. Apply the following supportive care guidance for hepatic events:

- For **Grade 2** events, monitor liver function tests more frequently until returned to baseline values (consider weekly).
 - Treat with IV or oral corticosteroids.
- For **Grade 3-4** events, treat with IV corticosteroids for 24 to 48 hours.
- When symptoms improve to Grade 1 or less, a steroid taper should be started and continued over no less than 4 weeks.

6.9.1.3.7. *Renal Failure or Nephritis - Pembrolizumab*

Apply the following supportive care guidance for renal failure or nephritis:

- For **Grade 2** events, treat with corticosteroids.
- For **Grade 3-4** events, treat with systemic corticosteroids.
- When symptoms improve to Grade 1 or less, steroid taper should be started and continued over no less than 4 weeks.

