6.6.2. Pembrolizumab Dose Delays and Discontinuation

Adverse events (both nonserious and serious) associated with pembrolizumab exposure may represent an immunologic etiology. These AEs may occur shortly after the first dose or several months after the last dose of treatment. Pembrolizumab must be withheld (dose reductions are not permitted) for drug-related toxicities and severe or life-threatening AEs. See Section 6.9.1.3 for supportive care guidelines, including use of corticosteroids. [Table JVDF.5](#) presents the guidelines for treatment delays and discontinuation of pembrolizumab for specific AEs associated with pembrolizumab treatment.

Table JVDF.5. Pembrolizumab Treatment Discontinuation Guidelines for Specific Adverse Events at Least Possibly Related to Pembrolizumab

	Adverse Event	CTCAE Grade	Treatment Delay and Discontinuation
1	Diarrhea/Colitis	2-3	
Delay pembrolizumab until resolved to Grade 0-1.
 
 • If resolved to Grade 0-1 within 12 weeks of last dose, then resume pembrolizumab. • Within 12 weeks of last dose, if toxicity does not resolve to Grade 0-1 *or* with inability to reduce corticosteroid to ≤ 10 mg/day of prednisone or equivalent per within 12 weeks, discontinue pembrolizumab.
		4	Immediately and permanently discontinue pembrolizumab.
2	Increased AST, ALT, or Bilirubin^a	2	
Delay pembrolizumab until resolved to Grade 0-1.
 
 • If resolved to Grade 0-1 within 12 weeks of last dose, then resume pembrolizumab. • If NOT resolved to Grade 0-1 within 12 weeks of last dose, then discontinue pembrolizumab.
		3-4	Immediately and permanently discontinue pembrolizumab. See exceptions below.
3	Type 1 Diabetes Mellitus (if new onset) or Hyperglycemia associated with evidence of beta cell failure	T1DM or 3-4	
Delay pembrolizumab until patients are clinically and metabolically stable.
 
 • If clinically and metabolically within 12 weeks of last dose, then resume pembrolizumab. • If NOT clinically and metabolically stable within 12 weeks of last dose, then immediately and permanently discontinue pembrolizumab.

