- The timing of the required 1-hour observation periods, to occur between ramucirumab and pembrolizumab administration *and* after pembrolizumab administration, for the first 2 cycles. Rationale: this change was implemented to ensure the consistent implementation of the 1-hour observation periods for Schedule 1 and Schedule 2 patients.
- Two additional categories of events are to be reported as SAEs: 1) new cancers (exception: metastases of cancer under study), and 2) any event associated with an overdose of either study drug, as defined in Section 8.2.1.2.
- For pembrolizumab, immune-related adverse events are no longer labeled as Events of Clinical Interest (ECIs). Similarly, references in the protocol to the detailed Site Guidance Document for Events of Clinical Interest were removed. Two (2) categories of ECIs remain: overdose and abnormal liver function tests (as defined in Section 8.2.1.1.3).
- Pembrolizumab dose modification table “Note” was updated to specify that Grade 2 pneumonitis warrants permanent discontinuation of pembrolizumab (see “Note” in table footnote).
- Pembrolizumab supportive care guidelines for Diarrhea/Colitis (Section 6.9.1.3.2) were updated to eliminate any waiting period before beginning treatment for any Grade 2, 3, or 4 event.
- Other typographical, formatting errors or very minor clarifications (key examples below):
 - The Introduction was updated to reflect current regulatory approval status for ramucirumab and pembrolizumab.
 - In Inclusion Criterion [7], to clarify that the screening period is 28 days.
 - Exclusion Criterion [20], to allow seasonal flu vaccines that do not contain live virus.
 - Dose management for ramucirumab in case of Grade 2 toxicity, investigator “may” reduce ramucirumab dose or discontinue ramucirumab. See footnote b in Table JVDF.4.
 - If radiologic imaging verifies initial progressive disease, tumor assessment should be repeated approximately (not “at least”) 4 weeks later to confirm PD.
 - That “whole” blood sample is collected for pharmacogenetic analysis where local regulations and ERBs allow.
 - That the overall response rates presented in the simulations represented by Table JVDF.8 and Table JVDF.9 are provided as a reference for estimation of statistical power rather than as a basis for any decision criteria.
 - A baseline brain scan by CT or MRI was added in the schedule of events (Attachment 1) to be consistent with inclusion criteria for NSCLC and urothelial cancer patients.

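### Protocol 6.9.1.3.2 places pembrolizumab-related Grade 2 diarrhea under two different steroid instructions, with nothing to say which applies

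*Protocol*

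**What the plan says.** Protocol 6.9.1.3.2 (Diarrhea/Colitis - Pembrolizumab) gives steroid guidance in consecutive bullets.

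- The first concerns "Grade 2 diarrhea/colitis". Sites are told to "administer oral corticosteroids (prednisone 1 to 2 mg/kg/day or equivalent").
- The second concerns "Grade 3 or 4 diarrhea/colitis (or Grade 2 diarrhea"); the words in its parenthesis, "or Grade 2 diarrhea", bring in the lower grade. Sites are told to "treat with intravenous steroids (methylprednisolone 125 mg) followed by high-dose oral steroids", the oral part being prednisone 1 to 2 mg/kg/day or dexamethasone.
- A third bullet then sets one taper, of at least 4 weeks, starting when symptoms have improved to Grade 1 or less. It makes no distinction between the two regimens.

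The introduction to 6.9.1.3 sets the scope for all of this: "The treatment guidelines are intended to be applied when the investigator determines the events to be related to pembrolizumab".

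**The concern.** The first two bullets are directive, and each names Grade 2 diarrhea. An investigator who judges such an event related to pembrolizumab can follow the first bullet exactly and give oral steroids, or follow the second exactly and start with an intravenous dose. Two sites could both comply and treat the same event differently.

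Two things are at stake. The first is patient safety, since the text gives a treating physician conflicting instructions for one event. The second is consistency. Safety and tolerability is the primary objective (Protocol Section 3), and this supportive-care section is meant to make toxicity management uniform across sites. Concomitant medications will be summarized and listed (SAP 5.3.4), so the steroid given should be visible in the data. Nobody reviewing those data could say, however, which route the protocol required.

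**Working it through.** No formula applies: the point contains no sample size, power, error rate or event count. The check is to map each event to the bullets and then look for any text that separates them.

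**Step 1. Map events to bullets in 6.9.1.3.2.**

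| Event (pembrolizumab-related) | Oral bullet | Intravenous bullet |
|---|---|---|
| Grade 2 colitis | yes | no |
| Grade 2 diarrhea | yes | yes |
| Grade 3 or 4 diarrhea/colitis | no | yes |

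Only Grade 2 diarrhea appears twice. Treating diarrhea without colitis as a separate category does not remove the overlap, because the oral bullet names both.

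**Step 2. Compare the two instructions.**

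| Element | Oral bullet | Intravenous bullet |
|---|---|---|
| Corticosteroids required | yes | yes |
| Initial intravenous methylprednisolone | no | yes, 125 mg |
| Oral prednisone range | 1 to 2 mg/kg/day | 1 to 2 mg/kg/day |
| Alternative to prednisone | an equivalent, not named | dexamethasone, with its own dose and interval |
| Taper | at least 4 weeks | at least 4 weeks |

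The instructions differ in the intravenous step and the dexamethasone alternative.

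**Step 3. Look for a rule that separates them.**

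- *Within the bullets.* Neither has a condition on duration, persistence, severity within grade, or failure of a first treatment.
- *Introduction to 6.9.1.3.* Relatedness to pembrolizumab triggers both bullets equally. The text mentions oral and intravenous corticosteroids as options where appropriate, but gives no rule for choosing.
- *Section 6.6.2 and Table JVDF.5.* The table has one row for Grade 2-3 diarrhea/colitis and governs delay and discontinuation of pembrolizumab. For steroid treatment the section sends the reader back: "See Section 6.9.1.3 for supportive care guidelines, including use of corticosteroids".
- *Attachment 7.* It permits systemic glucocorticoids for events of suspected immunologic origin, without distinguishing route.
- *SAP.* It contains no steroid-management rule.

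No passage resolves the overlap.

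**Step 4. Compare with the other events in 6.9.1.3.** Pneumonitis, hypophysitis, hyperthyroidism, hepatic events and renal events each keep Grade 2 apart from Grade 3-4. For Grade 2 hepatic events the protocol leaves the route open and says so. Diarrhea is the only event whose Grade 2 form is also named in the Grade 3-4 instruction.

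**The case against.** The strongest reply is that this section offers guidelines. Its introduction contemplates either route, and Grade 2 hepatic events may be treated by either, so leaving the route open at Grade 2 is not foreign to this protocol. Both bullets also lead to corticosteroids, the same prednisone range and the same taper, and Table JVDF.5 handles pembrolizumab identically whichever is followed.

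Much of this stands, and it limits the size of the point: the documents do not disagree on whether to treat, on the prednisone range or on the length of taper. It does not remove the contradiction. The diarrhea bullets are written as instructions, each for a named grade. Where the protocol intends a choice of route, as for hepatic events, it states the choice in one line. Here the reader meets two separate instructions and no statement that either will do.

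A reader might also infer that a duration condition once separated the bullets and was lost in amendment (b). The summary in Attachment 9 says that the guidelines for this section "were updated to eliminate any waiting period before beginning treatment for any Grade 2, 3, or 4 event". That history is plausible but cannot be established from the documents, and the summary describes superseded text. The point rests on the current wording alone.

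**Conclusion.** The contradiction holds. Pembrolizumab-related Grade 2 diarrhea is under two directive instructions, and nothing in the protocol or SAP chooses between them. The difference is confined to the initial intravenous methylprednisolone step and the dexamethasone alternative. The point deserves correction because it concerns a treatment instruction. It changes no sample size, power or endpoint calculation.

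Two stronger readings are tempting and are not supported.

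- *A patient count.* Protocol Table JVDF.1 gives 14% all-grade diarrhea with ramucirumab alone in gastric-GEJ cancer, and the Introduction lists diarrhea among pembrolizumab reactions seen in at least 20%. For a cohort of 25, a reader might compute 0.14 × 25 = 3.5 and 0.20 × 25 = 5 and take 3.5 to 5 as the number affected. That would be wrong. The first rate comes from patients who did not receive pembrolizumab, while these bullets apply only to pembrolizumab-related events. The second is a reporting threshold, so it is a floor and cannot serve as an upper end. Neither isolates Grade 2. The number affected cannot be derived from the documents.
- *An effect on tumor response.* A reader might infer that uneven steroid exposure between sites would alter response rates. No passage states or quantifies such an effect. The cohorts are open-label and analyzed separately with descriptive methods, so there is no randomized comparison to bias.

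The conclusion assumes only that the parenthesis means what it says. It is intact in the text and shows no sign of redaction or extraction damage.

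**What to change.** Reconcile the two bullets in Protocol 6.9.1.3.2. Either Grade 2 diarrhea is named under one instruction only, or the text states the condition that sends it to one bullet or the other. If a free choice of route is intended, one sentence should say so, as is done for Grade 2 hepatic events. Which of these is clinically right is for the sponsor's clinical team; this review takes no position on it.

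The cost is a wording change to one subsection, carried in the next amendment or a clarification to sites. The SAP, the sample size and the planned analyses need no change.
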